## **ABBREVIATIONS & DEFINITIONS**

ACR Albumin to Creatinine Ratio

AE Adverse Event

eSource Electronic source documents

GCP Good Clinical Practice

IC Informed Consent

ICH International Conference on Harmonization

IEC Independent Ethics Committee

IEC/IRB Independent Ethics Committee/Institutional Review Board

IVD In-Vitro Diagnostic

CKD Chronic Kidney Disease

Optima - URiSCAN Optima Urine Analyzer

## STUDY SYNOPSIS

Name of Device:	ACR   U.S. Urine Analysis Test System (henceforth ACR   U.S.)
Device Description:	The ACR   U.S. Urine Analysis Test System is an in-vitro diagnostic, home-use device for the semi-quantitative measurement of the Albumin-Creatinine Ratio (ACR). The device consists of a smartphone application, proprietary Color-Board and an ACR reagent strip. The device is available for prescription-use only. Results are intended to be used in conjunction with clinical evaluation as an aid in the assessment of kidney function.
Patient Population:	At least 250 male and female subjects, 18-80 years of age, patients with suspected or known urine detectable acute and chronic disease such as Diabetes Type 1/ Type 2, Hypertension, any kidney disease, subjects who are undergoing routine physical examinations, or healthy patients.
Structure:	A comparative, controlled, multi-centered, accuracy and usability study.
Objectives:	The objective of the study is to evaluate the performance of the ACR   U.S. in the hands of the potential lay user.
Primary Endpoint:	The degree of agreement of the ACR   U.S. (tested by a lay user) as compared to the URiSCAN Optima Urine Analyzer (tested by a healthcare professional), for the different concentrations (blocks) reported by the ACR   U.S. device.
Secondary Endpoint:	Evaluation of the ACR   U.S. usability, by potential lay user under actual use conditions of a simulated home environment.

Study Design:	
Eligible subjects meeting the pathological profile will be recruited at the designated site by the study personnel. Following subject consent, the subjects will be evaluated for eligibility based on their health condition and history.
 
The ACR   U.S. kit, in its original packaging, along with the ACR   U.S. smartphone application will be provided to the subject in a simulated home- use environment. All subjects will be provided with a list of tasks to complete, including providing a urine sample and operating the ACR   U.S. device on both an iPhone 11 device and a Google Pixel 3a mobile phone. After completing the test, the lay user will complete a post-test questionnaire. The study observer will also complete a questionnaire to collect information regarding the lay users' use of the ACR   U.S.
 
The device use will be compared with identified risks to determine if the percentage of failures is acceptable. Additionally, measurable usability criteria for specific, critical steps will be evaluated.
 
Following the usability test performed by the lay user, the subjects' urine samples will be tested by the study staff using the URiSCAN Optima Urine Analyzer. These results will be considered as the “true value”.

Data analysis:	
Results from the ACR   U.S. Urine Analysis Test System and the comparator device, the URiSCAN Optima Urine Analyzer, will be presented in tables listing the results in each group and the % exact match (agreement) and the % <math>\pm 1</math> block match.

Study Sponsor:	
Healthy.io Ltd.

Principal Investigators:	
[name] [name], [name],

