#### **4.1. Primary Objective**

The primary objective of the study is to evaluate the % exact match (agreement) and the %  $\pm 1$  block match (agreement) of ACR | U.S. (tested by the lay user) compared to the URiSCAN Optima Urine Analyzer (the comparator device, tested by a healthcare professional), for each tested concentration (block).

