### **6.1. Framework:**

- At least 250 patients will be recruited to participate
- Up to 15% of the samples may be spiked urine samples in case of insufficient native samples in certain blocks
- Multiple sites
- 2 mobile phones: iPhone 11 and Google Pixel 3a (per subject)
- 3 strip lots which will be used interchangeably throughout the experiment

**6.2. Population:** The study is a comparative, controlled trial of subjects who will be recruited from a research clinic. The study population will consist of patients with a medical history of diabetes Type I, Type II, Hypertension, kidney disease and other ailments that represent the target population for urine testing or healthy patients. The intention is to recruit subjects with ailments that will cover all test analytes and all concentrations of these analytes. In the case that analytes and concentrations will not be covered by enrolled subjects, the study will be supplemented with spiked urine samples with the missing analytes and concentrations. However, the number of spiked samples will not exceed 15% of the total samples (all bins combined). Lay users will test their own urine with both smartphones and additionally

may be asked to test another spiked sample, that will be provided by the study staff as necessary and in accordance to protocol.

**6.3. Testing Methods:** Subjects will be recruited for the clinical trials based on their ability to provide a urine sample and comfortably complete tasks using a smartphone. Each urine sample should be tested by a lay user on the ACR | U.S. app, and then transferred to a professional user to conduct the test on the Optima device. The professional user will be blinded to the results of the lay user until after they have completed the test using the Optima device.

**6.4. Timing:** Collection of a urine sample is performed by the patient as part of the study flow. Within 15 minutes from the time of patient's test, testing on the comparator analyzer should be done. This is to best simulate the real-case usage of the ACR | U.S. test. The specimen should not be centrifuged or refrigerated in between tests.

**6.5. Analyzers:** Each urine sample will be tested using the iPhone 11 and Google Pixel 3a devices running the ACR | U.S. application. Each test will be compared to the URiSCAN Optima Analyzer, the comparator device.

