**Figure 1 – Method Comparison Study Flow**

## 8. SUBJECT COMPLETION / WITHDRAWAL

### 8.1. Accuracy Evaluation

The ACR | U.S. test results will be compared to the Optima test results. The data will be graphically presented to compare the percent exact match (agreement) and the percent  $\pm 1$  block match (agreement) between the ACR | U.S. (tested by the lay user) and the comparator device (tested by a healthcare professional), for the different tested concentrations (blocks).

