### 10.2. Study Endpoints

- Primary Efficacy Endpoint

The primary endpoint of the study is to calculate the exact % match (agreement) and the %  $\pm 1$  block match (agreement) of the ACR | U.S. (tested by the lay user) compared to the URiSCAN Optima device (tested by a healthcare professional), ), for the tested concentrations (blocks).

- Secondary Efficacy Endpoint

The secondary endpoint of the study is to evaluate the ACR | U.S. usability, by potential lay users under actual use conditions (home environment).

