## **10.6. Statistical Analysis**

- General Considerations

Statistical analyses will be performed using an appropriate statistical program and methodology.

Baseline demographic and safety analyses will be performed on all enrolled subjects.

- Demographic and Other Baseline Variables

Demographic and baseline condition related characteristics will be tabulated. Continuous variables will be summarized by a mean, standard deviation, minimum, median and maximum, and categorical variables by a count and percentage.

- Disposition of Subjects

The number and percent of subjects who fail to complete the study and the number and percent of subjects who fail to complete the study because of Adverse Events will be presented.

- Efficacy Analysis

The % exact match (agreement) of the ACR | U.S. compared to the comparator device, for the same Albumin-Creatinine Ratio concentration (block) will be calculated. The %  $\pm 1$  block match (agreement) of the ACR | U.S. compared to the comparator device, for the same Albumin-Creatinine Ratio concentration (block) will also be calculated.

- Usability Analysis

The usability of the ACR | U.S. will be determined by evaluating the percentage of study subjects who are able to complete the device-related tasks, including accessing the ACR | U.S. App, providing a urine sample in the urine receptacle, dipping the kit urine strip in the urine specimen, positioning the strip on

the Color-Board and taking a picture using the smartphone App, with minimal attempts to ask for assistance.

Measurable usability criteria for specific, critical steps, such as time-to-completion, number of requests for assistance, numerical ratings, etc., will be evaluated by observer evaluation and user questionnaire responses. Descriptive statistics will be provided for usability criteria.

- Adverse Event

In general, there are no anticipated adverse events in this study; however, if any adverse events do occur they will be recorded and presented in tables.

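### Does it matter that the plan does not say whether per-block agreement is counted by Optima block or by test-device block, and plans no confidence interval or low/high count?

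*Combined protocol and SAP*

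**What the plan says.** The primary result is the percentage of exact matches and the percentage of matches within one block, by concentration block. The statements differ in how they refer to the blocks:

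- Synopsis, Primary Endpoint: agreement with the Optima "for the different concentrations (blocks) reported by the ACR" device, that is, the test device.
- Synopsis, Study Design, on the Optima readings: "These results will be considered as the" true value.
- Synopsis, Data analysis: results from both methods "will be presented in tables listing the results in each group", together with the two match percentages.
- Sections 4.1, 8.1 and 10.2: tested concentrations or blocks, without saying which method assigns the block.
- Section 10.6, Efficacy Analysis: the exact match of the test device "compared to the comparator device, for the same Albumin-Creatinine Ratio concentration (block) will be calculated", and likewise the match within one block.

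No confidence interval for agreement appears in the synopsis or in sections 4.1, 8.1, 10.2 or 10.6. Nor does a count of low and high misreads, a normal/abnormal cut-off, or an acceptance limit for agreement.

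Each subject uses two phones (6.1, 6.5) and may also be asked to test a spiked sample (6.2). Section 7.1 gives each enrolled subject a subject ID (Stage III). It gives the second kit a new ID so that the operator of the comparator stays blinded (Stage V, step 7).

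**The concern.** A per-block percentage has no meaning until its denominator is known. Counting within Optima blocks asks how often the device finds a sample's reference block. Counting within device blocks asks how often a reported block is right. The two can differ widely, and the synopsis wording can be read as asking for the second although the Optima is the stated truth.

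Exact and within-one-block percentages also hide direction. For a test that aids the assessment of kidney function, a sample read too low is not the same error as one read too high.

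Finally, there is no interval to show how weak the evidence is in a sparse block. Two results per subject under two kit IDs could also be analysed as if they came from two people. At stake would be what the primary tables say, not a pass/fail decision, because none is planned for agreement.

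**Working it through.** **What cannot be reproduced.** The plan's one relevant figure, at least 250 subjects (10.3), rests on earlier studies, a cited standard and experience. It has no error rate, target or precision from which to rebuild it. The number of blocks, their mix and the error rates are not given either, so every table below is an assumption.

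**1. Denominator, no over-reads.** Assume 3 blocks, Optima counts 150/60/40, and 20% of blocks 2 and 3 read one block low.

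- Misreads: 0.20 × 60 = 12 go to block 1, and 0.20 × 40 = 8 go to block 2.
- Device totals: 150 + 12 = 162; 48 + 8 = 56; 32.
- By Optima block: 150/150, 48/60, 32/40 = 100/80/80%.
- By device block: 150/162, 48/56, 32/32 = 92.6/85.7/100%.
- Overall: exact (150 + 48 + 32)/250 = 92.0% and within one block 250/250 = 100%, under either denominator.

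The 100% in the top block is built in. With no over-reads, nothing can enter that device block wrongly, whatever the read-low rate.

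**2. Adding over-reads.** Let a share of blocks 1 and 2 also be read one block high. The top device block then holds 32 correct results plus that share of 60.

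| Over-read share | Top block, by Optima | Top block, by device |
|---|---|---|
| 0% | 32/40 = 80% | 32/32 = 100% |
| 5% | 80% | 32/35 = 91.4% |
| 10% | 80% | 32/38 = 84.2% |
| 15% | 80% | 32/41 = 78.0% |

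**3. Another assumed error pattern.** Let 88% of Optima block 3 be read correctly, with 10% of block 2 and 1% of block 1 read as block 3.

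| Optima counts | Top block, by Optima | Top block, by device |
|---|---|---|
| 150/75/25 | 88% | 22/(22 + 7.5 + 1.5) = 71.0% |
| 200/40/10 | 88% | 8.8/(8.8 + 4 + 2) = 59.5% |
| 83/83/84 | 88% | 73.92/(73.92 + 8.3 + 0.83) = 89.0% |

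The choice of denominator can therefore matter a great deal or hardly at all, and it has no fixed direction.

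**4. Direction.** In a middle block of 60 with 12 one-block misreads, low/high splits of 12/0, 6/6 and 0/12 all give 80% exact and 100% within one block. The two percentages alone cannot separate these. A cross-table of the counts can.

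**5. Intervals.** Wilson 95% interval: [p + z²/2n ± z√(p(1−p)/n + z²/4n²)] / (1 + z²/n), with z = 1.96 and p = 0.80. For 40 subjects with both phones' results in one block, effective n = 80/(1 + ρ), where ρ is the within-subject correlation.

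| Assumed block | Effective n | 95% interval |
|---|---|---|
| 40 subjects, one phone | 40 | 65.2–89.5% |
| 40 subjects, two phones, ρ = 0 | 80 | 70.0–87.3% |
| 40 subjects, two phones, ρ = 0.5 | 53.3 | 67.4–88.5% |
| 40 subjects, two phones, ρ = 1 | 40 | 65.2–89.5% |
| 10 subjects, one phone | 10 | 49.0–94.3% |

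Treating paired results as independent would narrow the interval from 24.3 points (89.5 − 65.2) to 17.3 points (87.3 − 70.0) at most. No section says that the phones will be pooled.

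**6. What an analyst would do with the text.** The Optima is the stated truth, and the endpoint and analysis statements set the device against it. The synopsis phrase about reported blocks can simply mean the list of blocks the device is able to report. Percentages within Optima blocks are therefore the ordinary reading. Tables of both methods' results by group are naturally laid out as a cross-table. With its counts, a reader can compute percentages by either denominator, the low and high misreads, and a one-phone interval where each subject contributes one result.

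**The case for a change.** The best case for a change is that these descriptive tables are the primary result. With no acceptance limit to discipline them, their definition should be fixed before the data are seen. The synopsis phrase does attach the blocks to the test device, and an analyst who took it literally could report different per-block figures that the overall percentages would not expose. The words about results in each group do not guarantee a cross-table. The edits would use data already collected. The comparator standard named in 6.7 cannot be relied on to fill the gap, because its content is not in the documents.

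Most of these facts stand: the denominator is nowhere stated, direction is not requested, and no interval is planned. They do not show that the plan as written would mislead. The literal reading of the synopsis conflicts with the Optima's status as the truth and is not the reading 10.6 favours. The missing intervals leave the plan descriptive, but it states no precision or error bar that could be wrong.

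The independence worry is weaker. Subject IDs are kept for the study records, and the second kit's new ID serves blinding. Step 7 also suggests a second Optima reading for the second kit, and pairing each kit with its own reading is the natural handling.

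**Conclusion.** No change follows. This is missing detail that analysts would fill sensibly: agreement by Optima block, shown in a table of both methods' results, with subjects identifiable by their subject ID. The denominator could move the top-block figure by 20 points under one set of assumptions (80% versus 100%) and by 1 point under another (88% versus 89%). Overall exact and within-one-block agreement do not move at all. No test, limit or sample-size claim about agreement depends on the choice.

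The conclusion assumes that the report shows the cross-classified counts, as the synopsis is most naturally read. Stating the denominator, the direction of misreads and an interval when the results are reported would be good practice. Leaving them out of the plan is not an error in it.

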## 1. INTRODUCTION

---

### 1.1. Urinalysis and Albumin-to-Creatinine Ratio Overview

Urinalysis is an array of tests performed on urine, and one of the most common methods of medical diagnosis. The target parameters that can be measured or quantified in a urinalysis test include many substances and cells, as well as other properties, such as specific gravity and pH. Urinalysis can be performed by using urine test strips, in which the test results can be measured on the basis of color changes. Other methods of urinalysis include light microscopy (1).

An Albumin-Creatinine Ratio (ACR) urine test strip is a basic diagnostic tool used to determine pathological changes in a patient's urine in standard urinalysis. A standard ACR urine test strip usually contains two different chemical pads or reagents which react (change color) when immersed in, and then removed from, a urine sample. The test can often be read after 60 seconds after immersion. Routine testing of the urine with ACR urine test strips is the first step in the diagnosis of a wide range of kidney diseases. The analysis includes testing for the Albumin and Creatinine, and then calculating the ratio between them.

Albumin is the single-most important protein that is pathologically present in the urine in most chronic kidney diseases. A properly-functioning kidney will permit extremely small amounts of Albumin to pass into urine, and thus even a minute presence – defined as a quantity greater than 30 mg/L – is a sign of a diseased or distressed kidney. Creatinine is a byproduct of muscle metabolism released into the urine at a constant rate; its level in urine is an indication of urine concentration. The Albumin-to-Creatinine Ratio measurement is a widespread and effective screen for the early stages of CKD, in most instances appearing before the reduction in the estimated glomerular filtration rate (or eGFR, which requires a blood test).

ACR urine test strips can be used in many areas of the healthcare chain including screening for routine examinations, treatment monitoring, self-monitoring by patients and/or general preventive medicine. The ACR urine test is an effective measurement to identify patients with early stages of Chronic Kidney Disease (CKD), when patients are often asymptomatic, which can reduce the risks of cardiovascular disease, End-Stage Renal Failure (ESRF), and death that are the hallmarks of a malfunctioning kidney. According to the Henry Ford Health System, only 5% of the general Medicare population undergoes a

---

 "Albumin-to-creatinine ratio (ACR) is the first method of preference to detect elevated protein."

See the [National Kidney Foundation's](https://www.kidney.org/kidneydisease/siemens_hcp_acr) website detailing the importance of the ACR test:  
[https://www.kidney.org/kidneydisease/siemens\\_hcp\\_acr](https://www.kidney.org/kidneydisease/siemens_hcp_acr)

screening urinalysis, while only 2% of high-risk subjects screened through a National Kidney Foundation initiative self-reported a history of kidney disease.

Healthy.io has developed the ACR | U.S. Urine Analysis Test System (ACR | U.S.). The ACR | U.S. is a semi-quantitative, prescription-based, in vitro diagnostic (IVD) home use device for the measurement of the ratio between albumin to creatinine in a urine sample using a single-wrapped ACR urine reagent strip (microalbumin/creatinine).

Automatic analysis of urine test strips using automated urine test strip analyzers is a well-established practice in modern day urinalysis. It guarantees rapid, standardized measurement and immediate reliable documentation of the result. Most of these urine analyzers are based on the technology of reflectance photometry while additional technologies such as microscopy or flow cytometry exist (performed directly on the urine specimen).

The basic elements of the reflectance photometry are based on the analysis of the intensity and color of light reflected from the reagent areas on a urinalysis test strip. Most of the automated urine analyzers are specifically intended for lab environments and are operated by professional users. In recent years, following the tremendous development in communication media (especially with mobile media) there is a shift from "in-clinic" testing to the home-use self-testing. This trend enables manufacturers to develop cost effective, reliable, easy-to-use, self-monitoring test methods, including urinalysis methods.

Healthy.io Ltd. employs computer vision technology to turn smartphones into clinical-grade diagnostic devices. Previously, the company developed a smartphone application containing image recognition software that enables users to remotely and independently perform a urinalysis test, the DIP | U.S. (510(k) clearance number: K173327). The DIP | U.S. device is a prescription, home-use device intended for the analysis of six urine analytes. The company also developed a point of care, prescription-only, professional-use smartphone application to test for microalbuminuria, the ACR | LAB device (510(k) clearance number: K182384). Building off this experience, Healthy.io developed the ACR | U.S. to test for the Albumin-Creatinine Ratio. Further details on the device components and functionality are described in the device description section below.

---

 [Chronic Kidney Disease](#). Henry Ford Health System. 2011.

 See the 510(k) Substantial Equivalence Determination Decision Summary:  
[https://www.accessdata.fda.gov/cdrh\\_docs/reviews/K173327.pdf](https://www.accessdata.fda.gov/cdrh_docs/reviews/K173327.pdf)

 [https://www.accessdata.fda.gov/cdrh\\_docs/reviews/K182384.pdf](https://www.accessdata.fda.gov/cdrh_docs/reviews/K182384.pdf)

## DEVICE DESCRIPTION

---

### 1.2. General

The ACR | U.S. is a prescription, in-vitro diagnostic, home-use device for the semi-quantitative measurement of the Albumin-Creatinine Ratio. The device comprises a kit with a urine receptacle, an ACR urine test strip, an absorbing pad, a Color-Board and a user manual. The device also consists of an easy-to-use smartphone application and image recognition algorithm.

The ACR | U.S., while also a photometric based device, employs a computer vision technique, executed on various hardware platforms, in an uncontrolled lighting environment, used by an untrained user. The test has no pre-calibration step. The calibration and test are executed simultaneously during each test individually. This is executed via a Color-Board, which is part of the user kit. Performing test calibration eliminates lighting variances & camera disruptions and delivers a semi-quantitative measurement.

The kit consists of five elements, which have been designed for easy usage in a home setting;

1. Urine receptacle
2. ACR urine test strip
3. Absorbing pad
4. Color-Board
5. User manual

